3.5.2 Secondary outcomes

Secondary endpoints are grouped into domains of conceptually related endpoints, and the outcomes will be analyzed adjusting for multiple comparison within domain using a Bonferroni correction. Table 8 provides the grouping of the secondary outcomes into domains, along with the observed outcome distributions, the minimum detectable effect size at 80% power and a family-wise error rate of 5%, and a reference effect size (if available). The vast majority of secondary outcomes are sufficiently powered to detect clinically meaningful effects or effects found in similar interventions.

Table 9: Minimum detectable effect size for secondary outcomes

Outcome	Observed distributions	Minimum detectable effect size	Reference effect size
Mental Health			
Access to MDD and/or PTSD treatment	
 • N=259 • 65.5% access treatment 	19.2 percentage points	None
Quality of care for MDD	
 • N=210 • 8.8% with quality care 	18.9 percentage point	16 percentage points for medication adherence ¹² at 3 months
Quality of care for PTSD	
 • N=300 • 9% with quality care 	15.3 percentage point	Expect similar to MDD
MDD remission	
 • N=405 • 16.0% remission 	15.0 percentage points	15 percentage points ¹³
MDD response	
 • N=405 • 26.2% response 	15.8 percentage points	20 percentage points from CALM ¹³ or 23 percentage points from STEPS-UP ¹¹
PTSD remission	
 • N=368 • 56.2% remission 	17.8 percentage points	Similar to MDD remission
PTSD response	
 • N=365 • 21.6% response 	17.7 percentage points	18 percentage points ¹¹

Active suicidal ideation	
• N=523• 24.2% at 6-months	14.5 percentage point	Any reduction
--------------------------	---	-----------------------	---------------

Substance Use

Opioid use frequency	
• N=523• Mean (sd) = 4.3 (9.6)	0.27 standard deviations; 2.6 raw scale	None
----------------------	---	---	------

Opioid overdose events	
• N=525• 2.1% at 6-months	5.9 pct point reduction	None
------------------------	--	-------------------------	------

Overall Health

Physical health functioning	
• N=525• Mean (sd) = 36.8 (12.0)	3.2 points	Similar to mental health functioning
-----------------------------	---	------------	--------------------------------------

Mental health functioning	
• N=525• Mean (sd) = 37.3 (13.0)	3.5 points	2.3 points ¹¹
---------------------------	---	------------	--------------------------

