9.4.2 ANALYSIS OF THE PRIMARY ENDPOINT(S)

This protocol provides a summary of the statistical analyses, and the SAP provides additional details.

- Buprenorphine access is a time-to-event outcome and will be compared between arms by fitting a Cox proportional hazard regression model. Specification of the model is available in the SAP.
- Days of cumulative buprenorphine treatment will be compared between arms by fitting a linear regression model. Specification of the model is available in the SAP.
- Depression symptom severity and PTSD symptom severity are ordinal scales and will be analyzed using non-response weighted linear regression models. Additional model details and specification of covariates are provided in the SAP.

The primary analyses will be performed for the intention-to-treat population, which consists of all randomized subjects. Procedures for handling missing data are provided in the SAP.

A union-intersection test will be used to test the overall success of the study that combines the four primary outcomes into a single composite hypothesis. In particular, the null hypothesis is the intersection of the four primary outcome null hypotheses (i.e., all null hypotheses are true), and the alternative is the union of the alternative hypotheses (i.e., at least one alternative hypothesis is true). A Bonferroni or Benjamini-Hochberg correction on the individual hypotheses will be used to control the error rate of this composite test. The four primary hypotheses will be analyzed with a Type I error of 1.25%, which accounts for the multiple primary outcomes using a Bonferroni correction to control the family-wise error rate at 5% ($0.05/4 = 0.0125$).

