2.5 Definitions of outcomes

2.5.1 Primary outcomes

Table 1 defines the primary outcomes of this study. The hypotheses associated with these outcomes are as follows:

1. We hypothesize that patients with a new OUD episode of care who are randomized to CC-COD/CC-COD+ will receive buprenorphine within fewer days after that care episode

than new OUD patients who are randomized to enhanced usual care. Alternatively, the null hypothesis is that there will be no difference in the number of days until receipt of buprenorphine with a new OUD episode of care.

2. We hypothesize that patients who are randomized to CC-COD/CC-COD+ will have more days of buprenorphine treatment within 180 days of study enrollment than patients who are randomized to enhanced usual care. Alternatively, the null hypothesis is that there will be no difference in the number of days of cumulative buprenorphine treatment within 180 days of study enrollment.
3. We hypothesize that, among patients with probable depression at study enrollment, those who are randomized to CC-COD/CC-COD+ will have a greater reduction in depression symptoms 6 months after study enrollment compared to those who are randomized to enhanced usual care. Alternatively, the null hypothesis is that there will be no difference in depression symptoms 6 months after study enrollment among those with probable depression at enrollment.
4. We hypothesize that, among patients with probable PTSD at study enrollment, those who are randomized to CC-COD/CC-COD+ will have a greater reduction in PTSD symptoms 6 months after study enrollment compared to those who are randomized to enhanced usual care. Alternatively, the null hypothesis is that there will be no difference in PTSD symptoms 6 months after study enrollment among those with probable PTSD at enrollment.

A union-intersection test will be used to test the overall success of the study that combines the four primary outcomes into a single composite hypothesis. In particular, the null hypothesis is the intersection of the four primary outcome null hypotheses (i.e., all null hypotheses are true), and the alternative is the union of the alternative hypotheses (i.e., at least one alternative hypothesis is true). As described in subsequent sections, either a Bonferroni or Benjamini-Hochberg correction on the individual hypotheses will be used to control the error rate of this composite test.

Table 1: Definition of primary outcomes

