3.4.2 Overview and General Principles

The primary analyses will be performed for the intention-to-treat population, which consists of all randomized subjects. All individual statistical hypotheses will be tested using two-sided tests, with adjustment for multiple testing using a Bonferroni or Benjamini-Hochberg correction. Primary outcomes will be analyzed at a Type I error rate of 1.25% to control the family-wise error rate at 5% (e.g., so $0.05/4=0.0125$ when using a Bonferroni correction or the first p-value threshold for significance with Benjamini-Hochberg). Similarly, secondary and exploratory outcomes will be analyzed at Type I error rates to control family-wise error rate at 5% within domain. See Table 2 and 3 for definition of secondary outcome domains and our exploratory outcomes.

Outcomes derived from the follow-up surveys are subject to nonresponse, and statistical hypotheses based on these outcomes will be tested using nonresponse weighted models, if necessary. Traditionally, a logistic regression model can be specified predicting response using the demographic characteristics listed in Table , the baseline characteristics listed in Table , and the randomized treatment assignment. The model is given by:

$$\log \left(\frac{\Pr(R_{ij}=1)}{1-\Pr(R_{ij}=1)} \right) = \eta_j + \mathbf{X}_{ij} \boldsymbol{\theta} + \gamma T_{ij} + \rho P_{ij}$$

where η_j represent health system fixed effects. The nonresponse weight for participant i in health system j is given by $w_{ij} = \frac{1}{p_{ij}}$, where $p_{ij} = \Pr(R_{ij} = 1)$. However, we will utilize a nonparametric machine learner to estimate our nonresponse weights to allow for more complex relationships between the predictors variables and the odds of being a responder, thereby producing more high-quality nonresponse weights if they are deemed necessary.

To assess whether there is a need for use of nonresponse weights in our final analyses, we will assess how representative our sample of responders is for each outcome using effect sizes (ES) differences. If most of the ES differences are small (e.g., less than 0.1 or 0.2), we will feel good about the representativeness of our sample of responders to the original baseline sample and not utilize nonresponse weights in our final analyses.

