3.5 Statistical power

All calculations are for 80% power at a Type I error rate of 1.25%, which accounts for the multiple primary outcomes using a Bonferroni correction to control the family-wise error rate at 5% ($0.05/4 = 0.0125$). Actual calculations use the observed loss to follow up rate in the final sample.

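### Holm's step-down test would hold the same 5% family-wise error as the single-step Bonferroni named for the secondary domains and can only gain power; Bonferroni is valid, so this is an optional improvement

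*SAP*

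**What the plan says.** SAP 3.5.2 groups the secondary outcomes into domains and states that "the outcomes will be analyzed adjusting for multiple comparison within domain using a Bonferroni correction". Table 9 lists eight outcomes under mental health, two under substance use and two under overall health. SAP 3.4.2 sets the target: family-wise error of 5% within each domain. It also says "All individual statistical hypotheses will be tested using two-sided tests", "with adjustment for multiple testing using a Bonferroni or Benjamini-Hochberg correction". That sentence covers every hypothesis, so for secondary outcomes it is looser than 3.5.2. Protocol 9.4.3 requires adjustment within domain but names no method. Neither document mentions a step-down procedure.

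The primary family is worded differently. SAP 2.5.1 says "either a Bonferroni or Benjamini-Hochberg correction on the individual hypotheses will be used to control the error rate of this composite test", and Protocol 9.4.2 has nearly the same sentence before adding "The four primary hypotheses will be analyzed with a Type I error of 1.25"%. Bonferroni stands alone for the primaries only in that last Protocol sentence and in the power basis of SAP 3.5. The SAP's exploratory-outcomes section also allows either method.

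**The concern.** Single-step Bonferroni holds every outcome in a family of m at 0.05/m, even after some hypotheses have been rejected and no longer need protection. Holm relaxes the threshold as rejections accumulate and keeps the same error guarantee.

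The difference is largest where several effects are real together. The mental-health domain is a candidate: it is the largest family, and it includes remission and response on the same scale for both MDD and PTSD. Power is tight there by the plan's own reckoning. In Table 9 the detectable effect for quality of MDD care is 18.9 points against a reference effect of 16. For PTSD remission it is 17.8 points, against a reference described as similar to MDD remission, which is 15. What is at stake is power for secondary findings, not the validity of any test.

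**Working it through.** **Inputs.** From SAP Table 9: domain sizes 8, 2 and 2, with the N, SD or rate of each outcome. From SAP 3.4.2: two-sided tests and 5% family-wise error within domain. From SAP 3.5.2: 80% power. From SAP 2.7: 1:1 allocation. The documents give neither the correlation between outcomes nor the number of real effects, so both are assumptions here and are varied.

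**1. Reproduce the plan's detectable effects.** Per-test alpha is 0.05/8 = 0.00625 and 0.05/2 = 0.025.

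- Continuous outcomes: MDE = (2 × SD/√N) × (z(1−α/2) + z(0.80)). Mental health functioning: (2 × 13.0/√525) × (2.241 + 0.842) = 1.135 × 3.083 = 3.50 (stated 3.5). Physical functioning gives 3.23 (stated 3.2) and opioid use frequency 2.59 (stated 2.6).
- Binary outcomes: two-proportion test with pooled variance, solved upward from the observed rate. MDD remission (N = 405, 16.0%) gives 15.0 points (stated 15.0), quality of MDD care 18.9 (18.9), quality of PTSD care 15.3 (15.3), suicidal ideation 14.5 (14.5), access 19.1 (19.2), PTSD remission 17.7 (17.8) and overdose 5.9 (5.9).
- Two rows do not reproduce this way: MDD response (16.9 against 15.8) and PTSD response (17.1 against 17.7).

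Ten of twelve rows agree to within rounding or 0.1 point, so the table rests on single-step Bonferroni with m = 8, 2, 2.

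**2. Holm's thresholds.** Order the p-values and compare them with 0.05/m, 0.05/(m−1), …, 0.05, stopping at the first failure. The first threshold is Bonferroni's and each later one is larger. Everything Bonferroni rejects is therefore rejected, and the chance of at least one rejection is identical.

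**3. Two-outcome domain, by hand (independent tests).** For 80% power at 0.025 the test statistic is centred at 2.241 + 0.842 = 3.083. Its power at 0.05 is Φ(3.083 − 1.960) = 0.869. An outcome is rejected under Holm if p ≤ 0.025, or if 0.025 < p ≤ 0.05 and the other outcome has p ≤ 0.025.

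- Both effects real: 0.80 + (0.869 − 0.80) × 0.80 = 0.855.
- One effect real: 0.80 + (0.869 − 0.80) × 0.025 = 0.802.

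**4. Simulation** (400,000 draws, equicorrelated two-sided z-tests, each real effect at 80% power under Bonferroni). Average power per real effect:

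| Family | Real effects | Bonferroni | Holm, correlation 0 | Holm, correlation 0.5 |
|---|---|---|---|---|
| m = 8 | 1 | 80% | 80% | 80% |
| m = 8 | 4 | 80% | 83% | 83% |
| m = 8 | 6 | 80% | 87% | 85% |
| m = 8 | 8 | 80% | 92% | 89% |
| m = 2 | 1 | 80% | 80% | 80% |
| m = 2 | 2 | 80% | 86% (85.5) | 85% |

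Simulated family-wise error under Holm was at most 4.9%.

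**5. Detectable effects under Holm.** First-step values are unchanged. Only at the last step (alpha 0.05) do they fall fully: mental health functioning to 1.135 × (1.960 + 0.842) = 3.18, and MDD remission from 15.0 to about 11.5 points. Even 3.18 stays above the 2.3-point reference in Table 9.

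**The case against.** The strongest reply is that nothing is wrong. Prespecified Bonferroni within domain delivers the promised error rate, nearly all the detectable effects reproduce under it, and its simultaneous intervals agree with its tests, which is a legitimate reason to choose it. Holm gains nothing until another outcome in the same domain has been rejected, and the larger gains need most or all effects to be real. All of this stands, and it sets the grade of the point.

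A reader might infer more than the documents support:

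- **That the primary and exploratory families are also fixed as Bonferroni.** They are not. SAP 2.5.1, SAP 3.4.2, Protocol 9.4.2 and the SAP's exploratory section leave Bonferroni or Benjamini-Hochberg open. SAP 3.4.2 describes 1.25% as either the Bonferroni level or the first Benjamini-Hochberg threshold. Holm never rejects more than Benjamini-Hochberg, so lost power is not shown there.
- **That trial success is harder to reach.** Overall success is a union-intersection test needing at least one primary rejection. That chance is the same under Holm and Bonferroni.
- **That 797 enrolled against 1,200 measures the cost.** The 1,200 includes 300 targeted for the CR, which was sized on CC-COD+ against CC-COD. The primary calculations in Protocol 9.2 assumed 900.

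It might also be said that SAP 3.4.2 already allows something less strict through Benjamini-Hochberg. That method controls the false discovery rate. With eight independent tests and four real effects, its simulated family-wise error was 11.1%, so it does not meet the 5% family-wise promise.

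**Conclusion.** The point holds for the secondary domains as a near-free gain in efficiency, not as an error. Relative to 80% under Bonferroni, average power per real effect in the mental-health domain rises by about 0 points with one real effect, 3 with four, 5-7 with six and 9-12 with all eight. In a two-outcome domain the rise is about 0 with one real effect and about 5 with both. These figures assume that each real effect has exactly 80% power under Bonferroni and that all pairs of outcomes share one correlation between 0 and 0.5. The family-wise guarantee itself needs no assumption about correlation. It would be too strong to say that Bonferroni causes real effects to be missed: some may be, and only where several effects in one domain are real.

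**What to change.** Before unblinding, change the method named in SAP 3.5.2 from a Bonferroni correction to Holm's step-down procedure within domain. Make SAP 3.4.2 consistent by naming Holm for secondary outcomes and withdrawing the Benjamini-Hochberg option for them. Keep the Table 9 detectable effects and label them first-step values. Report Bonferroni-adjusted confidence intervals beside the Holm p-values.

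The cost is wording plus one small mismatch: those intervals correspond only to the first Holm step, so an outcome rejected at a later step may have an interval that includes no effect. Timing matters. SAP 2.2 says the plan was finalised before unblinding, and the documents do not show whether unblinding has since occurred. If it has, easing the thresholds would be a post hoc change; the prespecified Bonferroni results should then stand, with any Holm results labelled as supplementary.

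### SAP Table 9: the detectable effects for MDD response and PTSD response do not follow from the table's own sample sizes and rates

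*SAP*

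**What the plan says.** SAP section 3.5.2 groups the secondary outcomes into domains, to be analysed "adjusting for multiple comparison within domain using a Bonferroni correction". Its table (captioned Table 9) lists for each outcome the observed distribution, "the minimum detectable effect size at 80% power and a family-wise error rate of 5" per cent, and a reference effect where one exists.

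The two rows at issue are in the Mental Health domain:

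| Outcome | N | Observed rate | Stated detectable effect | Reference effect |
|---|---|---|---|---|
| MDD response | 405 | "26.2% response" | "15.8 percentage points" | 20 or 23 points |
| PTSD response | 365 | "21.6% response" | "17.7 percentage points" | 18 points |

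The text above the table concludes that nearly all secondary outcomes have enough power for effects that are clinically meaningful or have been seen with similar interventions. Section 3.4.2 sets the sidedness: "All individual statistical hypotheses will be tested using two-sided tests". The opening of section 3.5 also carries a general statement, "All calculations are for 80% power at a Type I error rate of 1.25" per cent, which it explains by the four primary outcomes.

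**The concern.** Comparing rows raises the doubt. MDD remission and MDD response have the same N (405) and sit in the same domain. Moving the rate from 16.0% to 26.2% brings it closer to 50% and raises the binomial variance, so the detectable effect should grow appreciably. The table raises it only from 15.0 to 15.8 points. The PTSD response figure, in contrast, looks too large for its N and rate.

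At stake is whether the power claimed for these two outcomes is what the SAP's own inputs deliver. If the effects are right, then an observed rate or an N in the table is wrong, and those entries summarise trial data.

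**Working it through.** **Inputs (all from the SAP)**
- Power 80% and family-wise error 5%, Bonferroni within domain (3.5.2). The Mental Health domain has eight outcomes, so per-test alpha = 0.05/8 = 0.00625. Two-sided (3.4.2), z = 2.734.
- Allocation 1:1 (2.7), so n per arm = N/2.
- N already reflects observed loss to follow-up (3.5), so there is no further inflation.

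**Formula.** Let p be the stated rate, q = p + d, and m = (p + q)/2.
- s0 = √[2m(1−m)/n]
- s1 = √[(p(1−p) + q(1−q))/n]
- Power = Φ[(d − 2.734·s0)/s1]

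The detectable effect is the d that gives power 0.80.

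**Step 1: reproduce the rows that work.** The SAP does not name its formula, so the convention was tested on the other binary rows first.

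| Outcome | N | Rate | Stated | Recomputed | Power at stated effect |
|---|---|---|---|---|---|
| Access to MDD/PTSD treatment | 259 | 65.5% | 19.2 | 19.1 | 80.5% |
| Quality of care, MDD | 210 | 8.8% | 18.9 | 18.9 | 79.9% |
| Quality of care, PTSD | 300 | 9% | 15.3 | 15.3 | 80.0% |
| MDD remission | 405 | 16.0% | 15.0 | 15.0 | 79.9% |
| PTSD remission | 368 | 56.2% | 17.8 | 17.7 | 80.6% |
| Active suicidal ideation | 523 | 24.2% | 14.5 | 14.5 | 80.1% |
| Opioid overdose (alpha 0.05/2) | 525 | 2.1% | 5.9 | 5.9 | 80.3% |

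Seven of the nine binary rows match to within 0.1 point.

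**Step 2: MDD response at the stated 15.8 points.** n = 202.5, p = 0.262, q = 0.420, m = 0.341.
- s0 = √(2 × 0.341 × 0.659/202.5) = 0.04711
- s1 = √((0.262 × 0.738 + 0.420 × 0.580)/202.5) = 0.04645
- (0.158 − 2.734 × 0.04711)/0.04645 = 0.628, so power = 73.5%

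Solving for 80% power gives 16.85 points before rounding (16.8). Detecting 15.8 points with 80% power would need N of about 458.

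**Step 3: PTSD response at the stated 17.7 points.** n = 182.5, p = 0.216, q = 0.393, m = 0.3045.
- s0 = √(2 × 0.3045 × 0.6955/182.5) = 0.04818
- s1 = √((0.216 × 0.784 + 0.393 × 0.607)/182.5) = 0.04728
- (0.177 − 2.734 × 0.04818)/0.04728 = 0.958, so power = 83.1%

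Solving for 80% power gives 17.1 points. Detecting 17.7 points would need N of only about 344.

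**Step 4: other methods.**

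| Method, alpha 0.00625 | MDD response, power at 15.8 | PTSD response, power at 17.7 |
|---|---|---|
| Pooled | 73.5% | 83.1% |
| Unpooled | 74.8% | 84.4% |
| Arcsine | 73.9% | 83.5% |
| Simulated logistic, Wald test | 73.3% | 82.8% |

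The variants tried also included a continuity correction, an analytic logit-Wald formula, an effect taken downward or centred on the observed rate, alphas of 0.0125, 0.05, 0.05/7, 0.05/12 and 0.05/13, and allocation from 45:55 to 55:45. Some rescue one row. For example, alpha 0.0125 gives MDD response 80.7%, and a continuity correction gives PTSD response 80.0%. None of the variants tried fits both.

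**Step 5: which input might be wrong.** At N=405, an effect of 15.8 points corresponds to a rate near 19.5%. At N=365, 17.7 points corresponds to a rate near 25.5%. Putting the MDD rate (26.2%) into the PTSD row gives 17.8 points at N=365 and 17.7 at N=368. Putting 21.6% into the MDD row gives 16.2, not 15.8, so a simple exchange of rates does not explain both cells.

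**The case against.** Four points can be made for the table.

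*A different alpha.* The opening of section 3.5 says all calculations use 1.25%. At that level MDD response has a detectable effect of 15.7 points and 80.7% power at 15.8. This may be how that one cell arose. It does not defend the table: at 1.25% the six matching Mental Health rows would have about 86% power, PTSD response 88.5%, and overdose 72%. The 1.25% is derived from the four primary outcomes, while section 3.5.2 sets its own within-domain rule, which the other rows follow.

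*Simulation.* Protocol section 9.2 describes power by simulation with 1,000 datasets. If that was also done here, the Monte Carlo standard error near 80% power is √(0.8 × 0.2/1000) = 1.3 points. PTSD response, 3.1 points away, is about 2.5 standard errors off, so chance is a strained but conceivable explanation. MDD response, 6.5 points away, is about 5 standard errors off and is not explained.

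*No consequence.* This largely stands. At 20 points MDD response has about 93% power, and at 18 points PTSD response has about 84.5%. The general statement that most secondary outcomes are adequately powered does not become false. The PTSD figure errs on the cautious side. The figures were computed after data collection ended, so the sample size does not depend on them.

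*The effect may not be the wrong entry.* This also stands. The documents do not show whether the effect, the rate, the N or the alpha is at fault.

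**Conclusion.** The concern holds. On the SAP's own N, rates and within-domain alpha, the detectable effect for MDD response is 16.8 points rather than 15.8, and power at the stated effect is about 74% (73.5% pooled, 74.8% unpooled) rather than 80%. For PTSD response it is 17.1 points rather than 17.7, with 83% to 84% power at the stated effect. Only the MDD response cell is optimistic, by about one point.

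This rests on a two-sided alpha of 0.05/8, equal arms, an increase from the stated rate, and no allowance for covariates in the logistic model. The SAP does not spell out this convention for the power calculation; it is inferred from the seven binary rows it reproduces.

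The matter is minor. It is a correction to a stated power figure and does not affect any analysis, population or decision.

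**What to change.** The sponsor should go back to the calculations for the two rows and confirm the N, the observed rate and the alpha that were used. If N and the rates are as printed, restate the detectable effects as 16.8 percentage points for MDD response and 17.1 for PTSD response. If a rate or an N is the wrong entry, correct that instead.

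Add a footnote to Table 9 giving the per-test alpha for each domain and the formula or simulation used, so that the 1.25% at the head of section 3.5 is not read as applying to secondary outcomes.

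The cost is two table cells and one footnote. With the printed inputs, one cell becomes slightly less favourable and the other slightly more.
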